2.8.4.2 Vital signs

Tables

Parameters to be summarized are the following:

- Change from baseline in body weight will be summarized by visit including last assessment on treatment and last assessment off treatment.
- Vital signs: clinically notable changes (Body weight change will also be split by weight loss and weight gain).

The number and percentage of participants with clinically notable vital signs abnormalities at any time post-baseline visit will be summarized. The criteria of clinically notable vital signs are provided in [Appendix 5.6](#).

Clinically notable weight changes of participants will be further investigated with the following summaries:

Frequency table will be presented for clinically notable weight changes (decrease/increase from baseline $\geq 7\%$ from baseline weight) during the treatment phase, by baseline weight categories (<55 kg, 55 - <70 kg, 70 - <84 kg, ≥ 84 kg) and by gender (Male, Female)

Participant demographics and other baseline characteristics with clinically notable weight decrease (loss) will be summarized.

Figures

For the following parameters, box-plots by visit will be created: Heart Rate, Systolic BP, Diastolic BP, body weight.

2.8.4.3 Prospective Suicidality Assessment

The Columbia-Suicide Severity Rating Scale (C-SSRS) is a questionnaire that prospectively assesses Suicidal Ideation and Suicidal Behavior. The electronic version, the eC-SSRS will be administered as described in the visit schedule of the study protocols and may also include unscheduled visits. At the first time of administration of the eC-SSRS, a retrospective assessment of suicidal behavior and ideation will be collected across lifetime. This data will be used to check inclusion/exclusion criteria. At all other scheduled assessments of suicidal behavior and ideation, any occurrence since the last visit will be collected.

The data will be reported by analysis period. The following three periods have been identified to cover lifetime history, the time between collection of lifetime history and start of study drug intake, and the time on study drug.

Tables

The number and percentage of participants pertaining to each of the categories of suicidal ideation and behaviors will be presented by analysis period and treatment.

The analysis periods will be defined as follows

1. Lifetime history: Lifetime assessment occurs only once (Screening 1 visit (Visit 101)).
2. Post disclosure pre-treatment period: assessments after the Screening 1 visit up to and including the baseline visit (Visit 103, Visit 107 and Visit 201 and unscheduled visit falling into this time period)
3. Post baseline: all visits after baseline visit (including unscheduled).

The summaries will show numbers and percentages of participants who have an answer “yes” to a suicidal behavior or ideation category at any time within the corresponding analysis period.

Listings

For participants with any assessment that meets the criteria to trigger the recording of an SAE as specified in the study protocols, a full listing will be presented. The criteria for SAE reporting are as follows:

If, at any time, the score is “Yes” on item 4 or item 5 of the Suicidal Ideation section of the C-SSRS or “Yes”. All such cases regardless of whether there was an SAE reported or not will be listed.

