5.6.5 Early study termination by the sponsor

Novartis may terminate the trial for reasons related to the benefit/risk assessment of treatment for participants in the study, or for regulatory or medical reasons (including slow enrollment) in consultation with the DMC. In the event that the study is terminated early, the HAs and IRBs/ECs will be informed on reasons for early termination and the process to prematurely withdraw the participants. In general, the participant should be seen as soon as possible and assessed as a prematurely withdrawn participant from the study. The withdrawal process may include additional procedures to be followed, in order to ensure that adequate consideration is given to the protection of the participant's interests.

6 Visit schedule and assessments

A preliminary step may be performed to obtain a buccal swab for APOE genotyping to be recorded in the local site database using the dedicated ICF#A. (refer to [Appendix 4](#))

[Table 6-1](#) lists all of the assessments and indicates with an “x” when the visits are performed.

Participants must be seen for all visits during the designated period, or as close to it as possible. Scheduled study visits during the treatment epoch may require multiple visits spread over different days that should be scheduled within the ± 4 -week window (exception for the cognitive assessments at month 3 XXXXXXXXXX, see [Table 6-1](#), footnote 45). Missed or rescheduled visits or assessments should not lead to automatic discontinuation. Upon study drug discontinuation, all dispensed investigational product should be reconciled.

Participants are encouraged to continue attending study visits even after study drug discontinuation. After the Early Termination of the treatment per the 11 July 2019 USM notification, mEoS visits can be scheduled any time after receipt of the Follow-up #2 notification but no later than 15-Mar-2020, and may be converted to a phone call in case of logistical constraints.

All adverse events and concomitant medications should be reconciled on the eCRF prior to End of Study (EoS).

Epoch	Screening ²							Treatment												
Visit Name	Scr1	Scr2	Scr3	Scr4	Scr5	Scr6	Scr7	Bas	Y1Q1 ₃₉	Y1Q2	Y1Q3	Y1Q4	Y2Q1	Y2Q2	Y2Q3	Y2Q4	Y3Q1	Y3Q2	Y3Q3	Y3Q4
Visit Numbers	101	102	103	104	105	106	107	201	202	203	204	205	206	207	208	209 ⁴⁰	210	211	212	213
Weeks									13	26	39	52	65	78	91	104	117	130	143	156
CDR, ECog ^{19,21,20,18}			X							X		X		X		X		X		X

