For efficacy parameters: In case of competing assessments within a visit window, the assessment value closest to the scheduled visit day will be used. In case of equal distances, the earliest assessment value will be used. Visit window will not be applicable for TEC and EoS.

For safety parameters: In case of competing assessments within a visit window, the worst assessment value within the visit window will be used. This rule also applies for worsening in cognition as a safety measure.

Listings will include all assessments, sorted by date of assessment, flagging unscheduled visits. The listings will include analysis windows and corresponding flags to indicate the assessment's inclusion in the analysis.

Treatment Epoch Completion (TEC) and End of Study (EoS) and other points in time of interest

TEC is the end of treatment phase visit (i.e., visit 299) that will be completed for all participants after discontinuation of treatment. The same visit will also be completed in case of PPW. PPW is the premature study withdrawal.

EoS is a Follow-up visit scheduled after TEC/PPW, per urgent safety measure (USM) on 11-Jul-2019, and its follow-up letter dated 12-Dec-2019, Modified EoS visits can be scheduled anytime after receipt of this notification but no later than 15-Mar-2020. (i.e. the requirement from 11 July 2019 USM for the 6 month timeframe between modified TEC and mEoS visits is no longer required.).

Participants who were attending study visits (i.e., continuing in the study) but already off-treatment at time of USM were to come for EoS straight (no TEC required).

An assessment will be on treatment if it is before or at last day on study drug + 31 days. The last assessment before or at last day on study drug + 31 days will be referred to as "last on treatment" assessment. The last assessment after last day on study drug + 31 days will be referred to as "last off treatment" assessment. For deriving "last on treatment" or "last off treatment", last assessment date of RBANS will be used. That means, to derive the last on treatment and last off treatment for all the parameters, regardless of their actual assessment

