2.8.1 Adverse events (AEs)

Treatment-emergent AEs (TEAEs) are events that either started after the first dose of study drug or events present prior to the start of study drug but increased in severity since the first dose. Adverse events reported within 31 days (5 half-lives) from study drug discontinuation date (i.e., last dose date) will be considered as TEAE. AEs reported more than 31 days after study drug discontinuation will not be considered treatment emergent (non-TEAE).

TEAEs and non-TEAEs will be summarized separately on the SAF.

Tables

TEAEs, SAEs, deaths and non-TEAEs will be summarized as follows

- TEAEs regardless of relationship to study drug by SOC, PT and maximum severity
- non-TEAEs, regardless of relationship to study drug by SOC and PT
- TEAEs causing study drug discontinuation by SOC, PT and maximum severity
- TEAEs related to study drug by SOC, PT and maximum severity
- TE-SAEs regardless of relationship to study drug by SOC and PT and maximum severity

Note: For missing information on AE relationship to study drug, the most conservative approach will be considered: If information on relationship of the AE to study drug is missing, the AE will be considered as related to study drug for reporting TEAEs.

The above summaries are generally without exposure adjustment, except from TEAEs by SOC and PT: this summary will be presented with exposure adjustment. The exposure-adjusted incidence rate of adverse events is defined as the number of participants with the adverse event divided by total participant years at risk in the treatment group. The time at risk for each participant will differ for each adverse event. For participants with events, only the time until the first event contributes to the total participant years at risk. For participants who do not experience the event, the time at risk will be calculated using the duration of exposure as defined in [Section 2.4.1](#). The exposure-adjusted incident rate will be summarized per 100 participant years. For participants with multiple occurrences of the same event, the event will be counted only once per participant.

Adverse events will be reported according to the latest MedDRA dictionary version available at the time of database lock.

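### The third eC-SSRS period is described as time on study drug but defined as every post-baseline visit, so the suicidality table pools on-drug and off-drug answers and cannot separate them

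*SAP*

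**What the plan says.** SAP 2.8.4.3 introduces three analysis periods and says what they stand for: lifetime history, "the time between collection of lifetime history and start of study drug intake, and the time on study drug". It then defines the third as "Post baseline: all visits after baseline visit (including unscheduled". The table counts, by period and treatment, participants who answered yes to a category at least once in the period. After the first administration, each scheduled questionnaire looks back to the previous visit: "any occurrence since the last visit will be collected".

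Elsewhere the SAP separates on-drug from off-drug data. Section 2.1.1 states: "An assessment will be on treatment if it is before or at last day on study drug + 31 days". Section 2.8.1 applies the same limit to adverse events: "AEs reported more than 31 days after study drug discontinuation will not be considered treatment emergent". It summarizes the later events separately. Section 2.8.4.2 reports body weight at the last on-treatment and last off-treatment assessments. Section 2.5.4 adds on-treatment versions of two time-to-event analyses.

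The eC-SSRS continues off drug. Protocol Table 6-1 schedules it at every visit in the treatment epoch, and at the mEoS visit if that is held on site. Protocol Section 6 allows mEoS visits after the second follow-up notification "but no later than 15-Mar-2020, and may be converted to a phone call in case of logistical constraints". Protocol 5.6.2 expects participants who stop drug to keep attending.

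**The concern.** The stated purpose and the rule cannot both hold once off-drug questionnaires exist. A reader who relies on the introductory sentence would take the third block of the table as on-drug experience, when it also holds answers about weeks or months after the stop.

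Suicidality is a named safety endpoint, and what happens after CNP520 is withdrawn is a central question of this abbreviated report. A single count of participants with any yes after baseline cannot show whether a report arose on drug or after stopping. The adverse event tables, shown by the same arms, do make that distinction, so the two safety outputs describe different periods.

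**Working it through.** **1. The SAP's own boundary.** Protocol 1.1 gives a mean terminal half-life of about 150 hours, and SAP 2.8.1 equates 31 days with five half-lives. 5 × 150 / 24 = 31.25 days, so the 31 days reproduces.

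**2. How far the third period can run past it.** The inputs are the stop instruction of 11-Jul-2019 (Protocol, Amendment 03), the second follow-up notification of 12-Dec-2019, the latest mEoS date of 15-Mar-2020 (Protocol Section 6 and SAP 2.1.1), and the example last dose of 09-Apr-2019 in SAP 2.1.1. A month is 365.25 / 12 days.

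| From last dose | To | Days | Months | Days beyond 31 |
|---|---|---|---|---|
| 11-Jul-2019 | 15-Mar-2020 | 248 | 8.1 | 248 − 31 = 217 |
| 11-Jul-2019 | 12-Dec-2019 | 154 | 5.1 | 154 − 31 = 123 |
| 09-Apr-2019 | 15-Mar-2020 | 341 | 11.2 | 341 − 31 = 310 |

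With a last dose on 11-Jul-2019, the on-treatment period closes on 11-Aug-2019. The 248 days is the maximum for those who stopped at the July notice. Earlier discontinuers can exceed it.

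Table 6-1 footnotes 42 and 43 give a shorter route: the modified treatment-completion (mTEC) visit at the next scheduled visit, then mEoS within 12 weeks. Assuming at most 13 weeks to the next visit, 13 × 7 + 12 × 7 = 175 days (5.7 months), still 144 days past the boundary.

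**3. Whether another rule closes the period.** SAP 2.8.4.3 has no off-treatment period. SAP 5.8 lists C-SSRS among the domains without analysis windows. The section's listing covers ideation items 4 and 5, and its remaining clause is incomplete in the text. Milder ideation is therefore not listed under that rule.

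**4. What pooling does to a comparison.** Let p1 and p0 be the proportions with an on-drug yes. Suppose off-drug time adds a similar proportion x in each arm, from participants with no on-drug yes. The difference (p1 + x) − (p0 + x) equals p1 − p0. The ratio (p1 + x) / (p0 + x) moves towards 1. Pooling adds participants and never removes one.

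**5. Where to cut, given recall since the previous visit.** Dispensing visits are three-monthly. If the next visit after the stop is uniformly spread over 91 days (assumption), 60 / 91 = 66% of mTEC visits fall after day 31. Each of those recalls back to a visit held on drug, so a cut on visit date would move on-drug reports to off treatment. The other 31 / 91 = 34% fall inside the window. A later on-site mEoS questionnaire whose previous visit was such an mTEC straddles the boundary. The start of the recall interval is therefore the safer criterion, with straddling assessments flagged.

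**The case against.** - **The label is honest.** The category is called post baseline, and that is what it contains. Only one sentence says otherwise, and rewording it would remove the contradiction. This stands as far as it goes, but rewording alone would leave the table unable to separate the two kinds of report.
- **Uncapped post-baseline summaries are common in this SAP.** Notable laboratory, ECG and vital-sign values are handled that way. True, but those sections do not claim to represent time on drug. This one does.
- **Part of the separation exists elsewhere.** Listings are ordered by time of assessment, and suicidality recorded as an adverse event passes through the 31-day split. This stands in part, since milder ideation appears in neither place unless it was also recorded as an adverse event.
- **The exposure to the problem may be small.** Telephone mEoS visits yield no eC-SSRS, and an mTEC visit within 31 days of last dose is on treatment by the SAP's definition. Both are correct. They limit the size, which the documents do not give.
- **The clinical stakes should not be stretched.** The 2018 safety measure added RBANS and NPI-Q, the 2019 stop concerned cognition, brain volume and weight, and the documents report no suicidality signal. This stands.

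**Conclusion.** The inconsistency is real and lies within one section. The third period does not deliver the period it is said to represent. Off-drug answers can enter it up to 248 days after the July 2019 stop (217 days beyond the SAP's window), and later still for earlier discontinuers. The dates come from the documents. The number of participants and reports affected does not.

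Three stronger readings are not supported:

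- That off-drug reports are shown as occurring on drug. The table label does not say so; that reading comes only from the introductory sentence.
- That pooling hides an on-drug difference. An any-time count keeps every on-drug case. Only a ratio shrinks, and an absolute difference is roughly unchanged if the additions are similar across arms.
- That about half of the recall time is typically off drug. That needs an on-site mEoS on the last allowed day and an assumed six months on drug: taking six months as 182 days, 217 / (182 + 248) = 50%. It is an extreme case.

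The correction is worth making because it is cheap and the SAP already holds the rule it needs.

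**What to change.** In SAP 2.8.4.3, keep the overall post-baseline count, so that no case drops out, and split it by arm:

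- **3a, on treatment:** assessments whose recall interval (since the previous visit) starts on or before last dose + 31 days. An assessment whose interval crosses that date stays here and is flagged, with the flagged count shown.
- **3b, off treatment:** assessments whose whole recall interval lies after last dose + 31 days.

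Amend the introductory sentence so that time on study drug refers to 3a, and the total is described simply as post baseline.

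The cost is a short SAP change and one or two extra table columns. No new data are needed: visit dates and last-dose dates are already used for the on-treatment derivation. The downside is that some straddling reports that arose off drug will stay in 3a. The flag shows how many, and erring in this direction avoids moving an on-drug report out of the on-treatment count.

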2.8.4.4 Safety MRI

Safety MRI findings will be summarized overall (at any visit) for ARIA-E, ARIA-H and White matter disease findings.

Worsening of white matter disease is defined on the age-related white matter changes rating Scale (ARWMC) which is rated on a 4 point (0-3) scale per region (bilaterally) on the following 5 different brain regions: Frontal Lobe, Parieto-Occipital, Temporal Lobe, Infratentorial area, Basal ganglia. ARWMC composite score is the sum of individual ARWMC scores from the 5 regions and ranges from 0 to 15. The ARWMC composite score will be used to summarize the white matter disease findings.

The definitions of the rating scores is shown in the below [Table 2-4](#).

Table 2-4 The ARWMC Rating Scale for MRI

Score	Definition
White matter lesions	
0	No lesions (including symmetrical, well-defined caps or bands)
1	Focal lesions
2	Beginning confluence of lesions
3	Diffuse involvement of the entire region, with or without involvement of U fibers
Basal ganglia lesions	
0	No lesions
1	1 focal lesion (≥5 mm)
2	>1 focal lesion
3	Confluent lesions

Tables

For ARIA-E, the following parameters will be presented

- Participants with any new ARIA-E (mild, moderate and severe) since Baseline,

For ARIA-H, the following parameters will be presented

- Participants with > 4 new microhemorrhages or any new macrohemorrhage \geq 10 mm in diameter since the Baseline MRI assessment

OR

- Participants with >10 microhemorrhages (new hemosiderin deposits < 10 mm) Or \geq 2 macrohemorrhages or \geq 2 areas of superficial siderosis (large area of hemosiderin deposition \geq 10 mm)

For white matter disease, the following parameters will be presented

- Participants with a white matter disease score increase since Baseline

Listings

Detailed safety MRI listings will be produced for participants with new occurrences or worsening (including Other MRI abnormalities) of identified findings.

The table content is redacted with black boxes.

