Summary statistics of change from baseline values will be presented by ECG parameter and treatment arm. Number and percentage of participants with clinically notable ECG abnormalities will be tabulated by treatment arm.

Safety brain MRI scans

Descriptive summaries will be provided by treatment arm for safety MRI data with special focus on ARIA and white matter disease. Number, intensity and location of microhemorrhages and white matter hyperintensities using the Wahlund scale (both as assessed by central MRI reader) will be tabulated.

Potential PD-mediated DDIs with frequent concomitant medications may include the use of medications which affect the coagulation/platelet function in terms of safety (e.g. increased incidence of ARIA-H). The effect of concomitant coagulation therapy and CNP520 on the risk of ARIA-H will be monitored by the DMC during the study, and analyzed by anticoagulant type and by their use during the study, using the information on timing of initiation and dose as time-varying covariates in the statistical TTE models.

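### The ARIA-H table in SAP 2.8.4.4 has no row for participants whose only new finding is 1-4 microhemorrhages or one area of superficial siderosis, although the protocol promises a microhemorrhage tabulation with no minimum count

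*SAP*

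**What the plan says.** Protocol 9.5.2, under safety brain MRI, sets the scope: "Descriptive summaries will be provided by treatment arm for safety MRI data with special focus on ARIA and white matter disease". It then commits to specific content: "Number, intensity and location of microhemorrhages and white matter hyperintensities using the Wahlund scale (both as assessed by central MRI reader) will be tabulated". No minimum number of lesions is attached to either sentence.

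SAP 2.8.4.4 opens broadly: "Safety MRI findings will be summarized overall (at any visit) for ARIA-E, ARIA-H and White matter disease findings". It then fixes what each table contains:

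- ARIA-E: "Participants with any new ARIA-E (mild, moderate and severe) since Baseline".
- ARIA-H, first criterion: "Participants with > 4 new microhemorrhages or any new macrohemorrhage" of at least 10 mm since the baseline MRI.
- ARIA-H, second criterion, joined to the first by OR: "Participants with >10 microhemorrhages (new hemosiderin deposits < 10 mm) Or" at least 2 macrohemorrhages, or at least 2 areas of superficial siderosis.
- White matter disease: any increase in score since baseline.

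On listings, the section says: "Detailed safety MRI listings will be produced for participants with new occurrences or worsening" of identified findings.

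**The concern.** Within one SAP section, ARIA-E and white matter disease are counted from the first new finding or any increase, while ARIA-H from microhemorrhages is counted only from the fifth new lesion. No reason is given for the difference. The protocol's undertaking on microhemorrhages has no such floor, and it covers location and intensity, for which the visible SAP table has no row.

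What is at stake is the by-arm safety summary. The study population is APOE4 carriers. Protocol 3.2 links that genotype to cerebral amyloid angiopathy and includes T2* gradient-echo sequences to monitor microbleeds. Protocol 9.5.2 also singles out ARIA-H in relation to medication affecting coagulation or platelet function. A difference between arms confined to low lesion counts, in either direction, would not show in the table as specified.

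**Working it through.** No sample size, power or error-rate figure is involved, so the check is a comparison of texts. The inputs are the two ARIA-H criteria and the listing rule in SAP 2.8.4.4, the tabulation commitment in Protocol 9.5.2, the rule on reporting MRI findings as adverse events in Protocol 6.4.7, and the record of changes in SAP Section 4.

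**Step 1. Apply both criteria to each possible isolated finding.** Call the criteria (a) (more than 4 new microhemorrhages, or a new macrohemorrhage of at least 10 mm) and (b) (more than 10 microhemorrhages, at least 2 macrohemorrhages, or at least 2 siderosis areas). Lesion counts are whole numbers, so more than 4 means 5 or more.

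| Only new finding | Meets (a) | Meets (b) | In ARIA-H table |
|---|---|---|---|
| None | no | no | no |
| 1, 2, 3 or 4 microhemorrhages | no | no | no |
| 5 to 10 microhemorrhages | yes | no | yes |
| More than 10 microhemorrhages | yes | yes | yes |
| 1 macrohemorrhage of at least 10 mm | yes | no | yes |
| 1 area of superficial siderosis | no | no | no |
| 2 or more areas of superficial siderosis | no | yes | yes |

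If the lesions counted in (b) are new ones, as its parenthesis indicates, anyone with more than 10 already satisfies (a). The microhemorrhage part of (b) then adds nobody when the two criteria are joined by OR, and the effective floor is 5. The gap is 1-4 isolated new microhemorrhages and a single new area of siderosis.

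**Step 2. Check the edges of the gap.** Someone with 1-4 new microhemorrhages does enter the table if another finding qualifies: a new macrohemorrhage of at least 10 mm, at least 2 macrohemorrhages, or at least 2 siderosis areas. If the count in (b) were read as cumulative, a high baseline count could also bring that person in, but the parenthesis points to new deposits.

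**Step 3. Look for another table that fills the gap.** Protocol 6.4.7 makes an MRI finding an adverse event only when it causes clinical signs or symptoms judged clinically significant. Adverse event tables will therefore not count silent microhemorrhages. The listings cover new occurrences, but a listing gives no count or percentage.

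**Step 4. Check whether the reduction is recorded.** SAP Section 4 names the changed safety set, the added mSAF, the dropped primary, sensitivity and supportive analyses, and the dropped MMRM analyses. Its visible text does not mention the MRI tabulation. One bullet in the list of analyses not performed is redacted.

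**The case against.** The strongest reply is that the narrowing was permitted. Amendment 3 leaves Protocol Section 9 untouched and defers changes caused by early termination to the SAP. Only an abbreviated report is planned, and SAP 2.8.4.4 states the reduced MRI content openly. The permission stands. It does not supply a reason for this reduction, because SAP Section 2 still undertakes to summarize all safety data descriptively by treatment group, and a descriptive lesion count does not depend on month-60 data.

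Several stronger readings are tempting, and the documents do not support them:

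- A reader might infer that the arms cannot be compared on new ARIA-H at all. New occurrences are listed, and SAP 2.1 orders listings by treatment group, so counts could be built by hand. The by-arm summary is missing, but the data are not.
- A reader might infer that everyone with 1-4 new microhemorrhages is treated like someone with none. They are listed, and those with another qualifying finding are tabulated.
- A reader might infer that Section 4 is silent. With a bullet redacted, only its visible text can be described.
- A reader might infer that the protocol expects microbleed harm. Protocol 3.2 offers only a tentative suggestion of benefit. SAP 2.5.4 notes that very few participants had data on active treatment beyond one year, so a slow benefit was unlikely to be visible.
- A reader might take the second ARIA-H criterion as a severe grade. In this section the SAP applies that word only to ARIA-E.

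The table shells are also unavailable and could hold more rows. The ARIA-H criteria in the SAP itself are, however, fully visible.

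**Conclusion.** The point holds in limited form. The visible ARIA-H table gives no by-arm count for participants whose only new finding is 1-4 microhemorrhages or one area of superficial siderosis, and it omits the location and intensity that the protocol said would be tabulated. Neither the SAP section nor the visible text of Section 4 explains this.

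The number of participants involved cannot be stated, because the documents contain no MRI counts. The effect is confined to one descriptive safety table. No primary, key secondary or inferential result depends on it. It is still worth correcting, because it determines what the reported safety summary can show about a finding to which the protocol gives special attention.

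The conclusion assumes that the unseen shells add no such rows, that the redacted bullet does not cover this tabulation, and that the second criterion counts new lesions, as its parenthesis says.

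**What to change.** Keep the existing ARIA-H rows and add, by treatment arm:

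- any new ARIA-H, defined as at least 1 new microhemorrhage, macrohemorrhage or area of superficial siderosis;
- 1-4, 5-10 and more than 10 new microhemorrhages;
- location of microhemorrhages, and intensity if the central reader recorded it.

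The bands follow the SAP's own cut-points of 4 and 10. They are a suggestion and not a protocol requirement, whereas number, location and intensity are protocol commitments. Any part of the protocol tabulation that will not be produced should be named in Section 4 with the reason.

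The cost is a few rows in one descriptive table, from scans already read centrally. The SAP's change history shows outputs added by addendum after database lock, so the route exists.
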